6.3.7 Events of Clinical Interest for Pembrolizumab

Selected non-serious and serious adverse events are also known as Events of Clinical Interest (ECI) and must be reported within 24 hours to the IND holder and within 2 working days to Merck Global Safety. [REDACTED]

For the time period beginning when the consent form is signed until the participant presents for cycle 1 day 1, any ECI, or follow up to an ECI, that occurs to any participant must be reported within 24 hours to the Sponsor and within 2 working days to Merck Global Safety ONLY if it causes the participant to be excluded from the trial, or is the result of a protocol-specified intervention, including but not limited to washout or discontinuation of usual therapy, diet, placebo treatment or a procedure.

For the time period beginning when the participant presents for cycle 1 day 1 through 90 days following cessation of treatment, or 30 days following cessation of treatment if the participant initiates new anticancer therapy, whichever is earlier, any ECI, or follow up to an ECI, whether or not related to Merck product, must be reported within 24 hours to the Sponsor and within 24 hours to Merck Global Safety.

Events of clinical interest for this trial include:

1. An overdose of Merck product., as defined in Section 6.1 - Definition of an Overdose for This Protocol and Reporting of Overdose to the Sponsor, that is not associated with clinical symptoms or abnormal laboratory results.
2. An elevated AST or ALT lab value that is greater than or equal to 3X the upper limit of normal and an elevated total bilirubin lab value that is greater than or equal to 2X the upper limit of normal and, at the same time, an alkaline phosphatase lab value that is less than 2X the upper limit of normal, as determined by way of protocol-specified laboratory testing or unscheduled laboratory testing.*

*Note: These criteria are based upon available regulatory guidance documents. The purpose of the criteria is to specify a threshold of abnormal hepatic tests that may require an additional evaluation for an underlying etiology.

6.4 Evaluating Adverse Events

An investigator who is a qualified physician will evaluate all adverse events according to the NCI Common Terminology for Adverse Events (CTCAE), version 4.0. Any adverse event which changes CTCAE grade over the course of a given episode will have each change of grade

recorded on the adverse event case report forms/worksheets.

All adverse events regardless of CTCAE grade must also be evaluated for seriousness as defined in Section 6.3.1. In addition, attribution of AEs must be classified based on the following definitions:

Definite – The AE *is clearly related* to the study treatment.

Probable – The AE *is likely related* to the study treatment.

Possible – The AE *may be related* to the study treatment.

Unlikely – The AE *is doubtfully related* to the study treatment.

Unrelated – The AE *is clearly NOT related* to the study treatment.

Table 15. Adverse Events Evaluation

An investigator who is a qualified physician, will evaluate all adverse events as to:

V4.0 CTCAE Grading	Grade 1	Mild; asymptomatic or mild symptoms; clinical or diagnostic observations only; intervention not indicated.
	Grade 2	Moderate; minimal, local or noninvasive intervention indicated; limiting age-appropriate instrumental ADL.
	Grade 3	Severe or medically significant but not immediately life-threatening; hospitalization or prolongation of hospitalization indicated; disabling; limiting self-care ADL.
	Grade 4	Life threatening consequences; urgent intervention indicated.
	Grade 5	Death related to AE
Seriousness	A serious adverse event is any adverse event occurring at any dose or during any use of Merck product that:	
	† Results in death ; or	
	† Is life threatening ; or places the participant, in the view of the investigator, at immediate risk of death from the event as it occurred (Note: This does not include an adverse event that, had it occurred in a more severe form, might have caused death.); or	
	† Results in a persistent or significant disability/incapacity (substantial disruption of one's ability to conduct normal life functions); or	
	† Results in or prolongs an existing inpatient hospitalization (hospitalization is defined as an inpatient admission, regardless of length of stay, even if the hospitalization is a precautionary measure for continued observation. (Note: Hospitalization for an elective procedure to treat a pre-existing condition that has not worsened is not a serious adverse event. A pre-existing condition is a clinical condition that is diagnosed prior to the use of a Merck product and is documented in the patient's medical history.); or	
	† Is a congenital anomaly/birth defect (in offspring of participant taking the product regardless of time to diagnosis); or	
	Is a new cancer (that is not a condition of the study) (although not serious per ICH definition, is reportable to the IND holder within 24 hours and to Merck within 2 working days to meet certain local requirements); or	
	Is an overdose (whether accidental or intentional). Any adverse event associated with an overdose is considered a serious adverse event for collection purposes. An overdose that is not associated with an adverse event is considered a non-serious event of clinical interest and must be reported within 24 hours to the Sponsor and to Merck within 2 working days.	
	Other important medical events that may not result in death, not be life threatening, or not require hospitalization may be considered a serious adverse event when, based upon appropriate medical judgment, the event may jeopardize the participant and may require medical or surgical intervention to prevent one of the outcomes listed previously (designated above by a †).	
Duration	Record the start and stop dates of the adverse event. If less than 1 day, indicate the appropriate length of time and units	
Action taken	Did the adverse event cause Merck product to be discontinued?	
Relationship to Merck Product	Did Merck product cause the adverse event? The determination of the likelihood that Merck product caused the adverse event will be provided by an investigator who is a qualified physician. The investigator's signed/dated initials on the source document or worksheet that supports the causality noted on the AE form, ensures that a medically qualified assessment of causality was done. This initialed document must be retained for the required regulatory time frame. The criteria below are intended as reference guidelines to assist the investigator in assessing the likelihood of a relationship between the test drug and the adverse event based upon the available information. The following components are to be used to assess the relationship between Merck product and the AE ; the greater the correlation with the components and their respective elements (in number and/or intensity), the more likely Merck product caused the adverse event (AE):	
	Exposure	Is there evidence that the participant was actually exposed to Merck product such as: reliable history, acceptable compliance assessment (pill count, diary, etc.), expected pharmacologic effect, or measurement of drug/metabolite in bodily specimen?
	Time Course	Did the AE follow in a reasonable temporal sequence from administration of Merck product? Is the time of onset of the AE compatible with a drug-induced effect (applies to trials with investigational medicinal product)?
	Likely Cause	Is the AE not reasonably explained by another etiology such as underlying disease, other drug(s)/vaccine(s), or other host or environmental factors

Relationship to Merck Product (continued)	The following components are to be used to assess the relationship between the test drug and the AE: (continued)	
	Dechallenge	Was Merck product discontinued or dose/exposure/frequency reduced? If yes, did the AE resolve or improve? If yes, this is a positive dechallenge. If no, this is a negative dechallenge. (Note: This criterion is not applicable if: (1) the AE resulted in death or permanent disability; (2) the AE resolved/improved despite continuation of the IND holder's product; or (3) the trial is a single-dose drug trial; or (4) IND holder's product(s) is/are only used one time.)
	Rechallenge	Was the participant re-exposed to Merck product in this study? If yes, did the AE recur or worsen? If yes, this is a positive rechallenge. If no, this is a negative rechallenge. (Note: This criterion is not applicable if: (1) the initial AE resulted in death or permanent disability, or (2) the trial is a single-dose drug trial; or (3) IND holder's product(s) is/are used only one time). NOTE: IF A RECHALLENGE IS PLANNED FOR AN ADVERSE EVENT WHICH WAS SERIOUS AND WHICH MAY HAVE BEEN CAUSED BY MERCK PRODUCT, OR IF REEXPOSURE TO MERCK PRODUCT POSES ADDITIONAL POTENTIAL SIGNIFICANT RISK TO THE PARTICIPANT, THEN THE RECHALLENGE MUST BE APPROVED IN ADVANCE BY THE IND HOLDER AS PER DOSE MODIFICATION GUIDELINES IN THE PROTOCOL.
	Consistency with Trial Treatment Profile	Is the clinical/pathological presentation of the AE consistent with previous knowledge regarding Merck product or drug class pharmacology or toxicology?
The assessment of relationship will be reported on the case report forms /worksheets by an investigator who is a qualified physician according to his/her best clinical judgment, including consideration of the above elements.		
Record one of the following	Use the following scale of criteria as guidance (not all criteria must be present to be indicative of Merck product relationship).	
Yes, there is a reasonable possibility of Merck product relationship.	There is evidence of exposure to Merck product. The temporal sequence of the AE onset relative to the administration of Merck product is reasonable. The AE is more likely explained by Merck product than by another cause.	
No, there is not a reasonable possibility of Merck product relationship	Participant did not receive the Merck product OR temporal sequence of the AE onset relative to administration of Merck product is not reasonable OR the AE is more likely explained by another cause than the Merck product. (Also entered for a participant with overdose without an associated AE.)	

Safety assessments will be based on medical review of AE reports and the results of vital sign measurements, physical examinations and clinical laboratory tests. The incidence of AEs will be tabulated and reviewed for potential significance and clinical importance. The reporting period for safety data will be from the date of first on-study dose to 70 days after the last dose is received. Additionally, from the time of consent forward, any occurrence of a serious adverse event (SAE) must be reported to the IND holder. The DSMC at DFCI will have oversight of this study.

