5.13 End of Treatment Evaluation and Follow-Up

The End of Treatment and Follow-up visit procedures are listed in Section 9 (Protocol Flow Chart) and Section 11 (Visit Requirements). After the end of treatment, each participant will be followed for 30 days for adverse event monitoring (serious adverse events will be collected for 90 days after the end of treatment as described in Section 6).

Participants who discontinue for reasons other than progressive disease will have post-treatment follow-up for disease status until disease progression, initiating a non-study cancer treatment, withdrawing consent or becoming lost to follow-up.

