From the time of cycle 1 day 1 through 30 days following cessation of treatment, all adverse events must be reported by the investigator. Such events will be recorded at each examination on the Adverse Event case report forms/worksheets. The reporting timeframe for adverse events meeting any serious criteria is described in section 6.3 The investigator will make every attempt to follow all participants with non-serious adverse events for outcome.

Adverse events will not be collected for participants during the pre-screening period (for determination of archival tissue status) as long as that participant has not undergone any protocol-specified procedure or intervention.

6.1 Definition of an Overdose for Pembrolizumab and Reporting of Overdose to the Sponsor and to Merck

For purposes of this trial, an overdose of pembrolizumab will be defined as any dose of 1,000 mg or greater (≥ 5 times the indicated dose). No specific information is available on the treatment of overdose of pembrolizumab. Appropriate supportive treatment should be provided if clinically indicated. In the event of overdose, the participant should be observed closely for signs of toxicity. Appropriate supportive treatment should be provided if clinically indicated.

If an adverse event(s) is associated with (“results from”) the overdose of a Merck product, the adverse event(s) is reported as a serious adverse event, even if no other seriousness criteria are met.

If a dose of Merck’s product meeting the protocol definition of overdose is taken without any associated clinical symptoms or abnormal laboratory results, the overdose is reported as a non-serious Event of Clinical Interest (ECI), using the terminology “accidental or intentional overdose without adverse effect.”

All reports of overdose with and without an adverse event must be reported within 24 hours to the IND holder and within 2 working days to Merck Global Safety. (Attn: Worldwide Product Safety; [contact])

6.2 Reporting of Pregnancy and Lactation to the Sponsor and to Merck and Amgen

Although pregnancy and lactation are not considered adverse events, it is the responsibility of investigators or their designees to report any pregnancy or lactation in a participant (spontaneously reported to them) that occurs during the trial.

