6.3 Immediate Reporting of Adverse Events to the Sponsor and to Merck

6.3.1 Serious Adverse Events

A serious adverse event is any adverse event occurring at any dose or during any use of Merck or Amgen products that:

- Results in death;
- Is life threatening;
- Results in persistent or significant disability/incapacity;
- Results in or prolongs an existing inpatient hospitalization;
- Is a congenital anomaly/birth defect;
- Is another important medical event

- **Note:** In addition to the above criteria, adverse events meeting either of the below criteria, although not serious per ICH definition, are reportable to the Sponsor, Merck and Amgen in the same timeframe as SAEs to meet certain local requirements. Therefore, these events are considered serious by Merck and Amgen for collection purposes.
 - Is a new cancer (that is not a condition of the study);
 - Is associated with an overdose.

For the time period beginning when the consent form is signed until the participant presents for cycle 1 day 1, any serious adverse event that occurs to any participant must be reported within 24 hours to the IND holder and within 2 working days to Merck Global Safety and Amgen ONLY if it causes the participant to be excluded from the trial, or is the result of a protocol-specified intervention, including but not limited to washout or discontinuation of usual therapy, diet, placebo treatment or a procedure.

Any serious adverse event, or follow up to a serious adverse event, including death due to any cause other than progression of the cancer under study that occurs to any participant from the time the participant presents for Cycle 1 Day 1 through 90 days following cessation of treatment, or the initiation of new anti-cancer therapy, whichever is earlier, whether or not related to Merck or Amgen product, must be reported within 24 hours to the Sponsor and within 2 working days to Merck Global Safety and Amgen. Additionally, any serious adverse event, considered by an investigator who is a qualified physician to be related to Merck product that is brought to the attention of the investigator at any time following consent through the end of the specified safety follow-up period specified in the paragraph above, or at any time outside of the time period specified in the previous paragraph also must be reported immediately to the IND holder and to Merck Global Safety.

All participants with serious adverse events must be followed up for outcome.

[REDACTED]

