10.5 Post Treatment Visits

10.5.1 Safety Follow-Up Visit

The mandatory Safety Follow-Up Visit should be conducted approximately 30 days after the last dose of trial treatment or before the initiation of a new anti-cancer treatment, whichever comes first. All AEs that occur prior to the Safety Follow-Up Visit should be recorded. Participants will be followed until the beginning of a new anti-neoplastic therapy. SAEs that occur within 90 days of the end of treatment or before initiation of a new anti-cancer treatment should also be

followed and recorded. Participants who are eligible for retreatment with pembrolizumab (as described in Section 10.5.4) may have up to two safety follow-up visits, one after the Treatment Period and one after the Second Course Phase.

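### The 70-day safety reporting period in Section 6.4 matches no collection rule: all adverse events are required to day 30, SAEs and events of clinical interest to day 90

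*Combined protocol and SAP*

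**What the plan says.** The closing paragraph of Section 6.4 describes how safety will be assessed, says incidence will be tabulated, and sets the window: "The reporting period for safety data will be from the date of first on-study dose to 70 days after the last dose is received".

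The collection rules are elsewhere:

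- **All adverse events.** Section 6: "From the time of cycle 1 day 1 through 30 days following cessation of treatment, all adverse events must be reported by the investigator". Section 5.13 agrees: "each participant will be followed for 30 days for adverse event monitoring". Section 10.5.1 ties recording to a visit about 30 days after the last dose, or earlier if new treatment starts: "All AEs that occur prior to the Safety Follow-Up Visit should be recorded".
- **SAEs.** Section 6.3.1 runs "through 90 days following cessation of treatment, or the initiation of new anti-cancer therapy, whichever is earlier". Section 5.13 gives 90 days and mentions no new-therapy cut: "serious adverse events will be collected for 90 days after the end of treatment as described in Section 6".
- **ECIs, which include selected non-serious events.** Section 6.3.7 gives 90 days, or 30 days if new therapy is started.
- **Follow-up.** Section 10.3.2.1 has adverse events recorded through follow-up with no day limit. The post-treatment calendar in Section 9 marks adverse event review at the 12-weekly Follow Up Visits but not under Survival Follow-Up.
- **Before the first dose.** Section 6.4 says that "from the time of consent forward, any occurrence of a serious adverse event (SAE) must be reported to the IND holder". Section 6.3.1 asks for a pre-dose SAE "ONLY if it causes the participant to be excluded from the trial" or if it results from a protocol-specified intervention.

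Section 14.7, the safety analysis section, summarises all adverse events recorded in the trial and names no cut-off day.

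**The concern.** Safety and tolerability are the primary objective of both parts (Section 1.2). A cumulative incidence needs a period over which the event in question was looked for in the same way in every patient. The only period the protocol states for safety reporting is one over which this does not hold.

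The tail of the window matters here. Section 5.3.3.1 warns that immune-related events may appear several months after the last dose. Section 14.7 halts expansion enrolment for review if two or more treatment-related late toxicities are seen, but gives no window for calling a toxicity late. If the 70-day sentence is followed as written, days 31-70 could read as fully observed for ordinary non-serious toxicity, and SAEs that sites did report on days 71-90 would be left out.

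Sites also have two incompatible instructions for SAEs between consent and first dose.

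**Working it through.** No power or error-rate figure is involved. The 70 days is a bare statement and cannot be derived from any other figure in the protocol. The check compares the windows.

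**Inputs (days after treatment ends)**

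| Rule | Ends at | Section |
|---|---|---|
| Safety reporting period | 70 | 6.4 |
| All adverse events | 30 | 5.13, 6, 10.5.1 |
| SAEs | 90 | 5.13, 6.3.1, 10.5.1 |
| ECIs | 90 | 6.3.7 |
| Safety Follow-up visit | 30 ± 3 | 9 |
| First Follow Up Visit | 84 ± 7 | 9, 10.5.2 |

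**Step 1: mismatch with each rule.**
- Routine non-serious events: 70 − 30 = 40 days (days 31-70), or 40/70 = 57% of the post-dose window.
- SAEs: 90 − 70 = 20 days (days 71-90) collected but outside the period.

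**Step 2: do follow-up visits fill days 31-70?** The Safety Follow-up visit is on day 30 + 3 = 33 at the latest. The first Follow Up Visit is on day 84 − 7 = 77 at the earliest and day 84 + 7 = 91 at the latest. No post-treatment adverse event review is therefore scheduled between about day 33 and day 77, and the next one comes after day 70. These visits are for participants who stopped for reasons other than progression (Section 10.5.2). After confirmed progression or new therapy, participants move to telephone contact for survival status (Section 10.5.3), where the calendar marks no adverse event review. Ascertainment on days 31-70 therefore differs between those who progressed and those who did not.

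**Step 3: anchor dates.** Section 6.4 counts from last dose, Sections 6 and 6.3.1 from cessation of treatment, Section 5.13 from end of treatment, and the calendar from discontinuation. Step 1 treats these as the same day. If cessation were recorded one 21-day cycle after the last dose (an assumption), the gaps would be 70 − (30 + 21) = 19 days and (90 + 21) − 70 = 41 days.

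**Step 4: the 40 days as a share of nominal time.** Share = 40 / (days on treatment + 70).

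| Time on treatment | Calculation | Share |
|---|---|---|
| 6 weeks | 40/(42 + 70) = 40/112 | 36% |
| 12 weeks | 40/(84 + 70) = 40/154 | 26% |
| 24 weeks | 40/(168 + 70) = 40/238 | 17% |
| 1 year | 40/(365 + 70) = 40/435 | 9% |
| 2 years | 40/(730 + 70) = 40/800 | 5% |

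The Study Summary gives an average treatment length of 1-2 years. Section 14.8 expects only about 40% of patients to complete 24 weeks. Both ends of the range are therefore relevant.

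**Step 5: new-therapy cut-offs.** Section 6 has none for all adverse events, and Section 5.13 has none for SAEs. Section 10.5.1 brings the safety visit forward if new treatment starts and ends SAE recording there. Section 6.3.1 ends SAE reporting at new therapy. Section 6.3.7 shortens ECI reporting to 30 days.

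**The case against.** The strongest reply is that Section 14.7 governs the safety tables and has no 70-day cut. It summarises every recorded event, so nothing there drops an SAE on day 80. This stands in part: the harm arises only if the Section 6.4 sentence is applied. But that paragraph itself speaks of tabulating incidence, no other safety reporting period is stated, and Section 14.7 does not say which rule prevails.

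A reader might infer that non-serious events on days 31-70 are simply not collected. The documents do not support that. Non-serious ECIs are reportable to day 90 unless new therapy starts, Section 10.3.2.1 continues recording into follow-up, and the calendar reviews adverse events every 12 weeks. The protocol contradicts itself on whether recording stops at day 30. What remains is that only SAEs and ECIs are clearly required in that interval.

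A reader might also infer that after early new therapy a non-serious event is reportable and a serious one is not. That fails. Section 6 asks for all adverse events to day 30, and Section 6.3.5 requires events reported by expedited routes to appear in routine submissions as well. Section 6.3.1 still requires SAEs judged related to the Merck product at any time.

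Finally, dose finding is unaffected, because DLTs are assessed in the first 3 weeks (Section 5.5). The pre-dose SAE conflict does not touch the incidence tables, which count events that start or worsen from first dose.

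**Conclusion.** The inconsistency is real and should be corrected. The 70-day period agrees with neither the 30-day nor the 90-day rule. The mismatch is 40 days for routine non-serious events and 20 days for SAEs, taking last dose and cessation as the same day. Incidence over 70 days would combine complete ascertainment to day 30 with partial ascertainment afterwards. The pre-dose SAE wording is a second, separate contradiction.

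The 5% to 36% shares are shares of nominal time, not estimates of bias. It would be tempting to read them as the understatement of incidence, but that needs no ascertainment at all on days 31-70, a constant event rate and rare events. Even with the first two granted, suppose 80% of patients have an event over 154 days. Incidence over 154 − 40 = 114 days would be 1 − 0.2^(114/154) = 69.6%, a shortfall of 1 − 69.6/80 = 13% rather than 26%. The actual bias cannot be computed from the documents.

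**What to change.** - **Section 6.4:** replace the 70-day sentence with one window per event class that matches the collection rules, counted from a single defined anchor date. Use that anchor wherever the windows appear.
- **Section 14.7:** tabulate all adverse events to last dose + 30 days, and SAEs and ECIs to last dose + 90 days, as separate tables. List any adverse events recorded later separately. A hard stop at day 30 would discard events that Sections 9 and 10.3.2.1 ask sites to record.
- **New-therapy cut-offs:** reconcile Sections 5.13, 6, 6.3.1, 6.3.7 and 10.5.1, and state the rule in each table's footnote.
- **Follow-up recording:** state what adverse event review at the 12-weekly visits is meant to capture, so that Sections 9 and 10.3.2.1 no longer conflict with the 30-day rule.
- **Pre-dose SAEs:** align the consent-forward sentence in Section 6.4 with Section 6.3.1.

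The cost is amendment text, with no new visits or data collection for the reporting windows. Aligning the new-therapy and pre-dose rules changes reporting instructions, so it needs agreement between the IND holder and the two companies.
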